7.10.2. Adverse Events

Reported adverse event (AE) terms will be mapped to MedDRA preferred terminology. AEs suggestive of tumor lysis syndrome (TLS) will be flagged based in the standardized MedDRA query (SMQ) for TLS. All reported events will appear in AE listings, however only treatment-emergent adverse events will be summarized. A treatment-emergent adverse event (TEAE) is an AE that starts or increases in severity any time after the first administration of any study drug up to 30 days following the last administration of any study drug. AE severity was rated by the investigator according to Common Terminology Criteria for Adverse Events (CTCAE) version 4.03 criteria.¹³

A high-level safety summary will display the numbers of patients within and across alvocidib dose levels who experience one or more AEs in each of the following categories:

- All TEAEs regardless of severity or presumed relationship to study drug
- TEAEs judged related to study drug
- All TLS SMQ TEAEs
- TLS SMQ TEAEs judged related to study drug
- Treatment-emergent serious adverse events (SAEs)
- TEAEs leading to a delay in the administration of study drug
- TEAEs leading to a reduction in the protocol-specified dose of study drug
- TEAEs leading to discontinuation of study drug
- TEAEs leading to withdrawal from the study
- TEAEs leading to death

The base summary of TEAEs will show incidence rates for each MedDRA primary SOC and/or PT by highest reported CTCAE severity grade and overall. A separate summary

will be produced each of the AE subsets listed above. Additional AE summaries may be produced using safety data from subsets of patients and/or characterized using additional SMOs.

Partial start and end dates for adverse events will be replaced by calendar dates that maximize the duration of the adverse event. The following steps will be followed.

For a partial start date:

- 1. Replace a missing month with January
- 2. Replace a missing calendar day with the first of the month
- 3. If the replacement date is prior to the first dose of study drug, then set the adverse event start date equal to the date of the first dose

For a partial end date:

- 1. Replace a missing month with December
- 2. Replace a missing calendar day with the last day of the month

The replacement date for a missing end date may exceed end of the adverse event reporting period specified in the study protocol.

An end date will not be estimated for adverse events marked continuing at the end of the study.

7.10.3. Classification of Tumor Lysis Syndrome

Cairo-Bishop definitions for laboratory TLS and clinical TLS will be used to diagnose and grade TLS.¹⁴ Patients are classified as experiencing laboratory TLS if they have any two or more serum values of uric acid, potassium, phosphorus and/or calcium shown in Table 2 within 3 days before or 7 days after the initiation of study drug.

Table 2. Cairo-Bishop Definition of Laboratory Tumor Lysis Syndrome

Laboratory Parameter	Criteria
Uric Acid	≥476 µmol/L or 25% increase from baseline
Potassium	≥6.0 mmol/L or 25% increase from baseline
Phosphorus	≥1.45 mmol/L or 25% increase from baseline
Calcium	≤1.75 mmol/L or 25% decrease from baseline

Diagnosis of clinical TLS requires the presence of laboratory TLS and elevated serum creatinine levels, cardiac arrhythmia and/or seizures. Criteria for grading the severity of clinical TLS are presented in Appendix 1.

The numbers of patients experiencing laboratory TLS and the various severities of clinical TLS will be summarized within and across alvocidib dose levels.

7.10.4. Clinical Laboratory Parameters

Within-cycle patient minimum and maximum laboratory values (and changes from baseline) for analytes measured on a continuous scale will be summarized within and across alvocidib dose levels using descriptive statistics appropriate for continuous variables (see section 7.6). Ordinal categorical test results will be summarized within

and across alvocidib dose levels using shift tables. Additionally, for tests where CTCAE [version 4.03] severity criteria are specified, CTCAE severity grades will be summarized in shift tables.

7.10.5. Neutrophil Recovery

Time to neutrophil recovery is defined for all patients and is measured from the date of first dose (Day 1) until the first day the absolute neutrophil count (ANC) is $\geq 1 \times 10^9 / L$ for 14 consecutive days. It is assumed that the ANC remains above the threshold value of $1 \times 10^9 / L$ unless there is evidence that it did not. Therefore, a patient with ANC $\geq 1 \times 10^9 / L$ on Day 45 and without another assessment for > 14 days will have a time to neutrophil recovery of 45 days.

Rules for censoring time to neutrophil recovery are:

- A patient with ANC <1x10⁹/L as of the date he is lost to follow-up will have his time to neutrophil recovery censored on the date of his last assessment of any type
- A patient with ANC <1x10⁹/L as of the database lock will have his time to neutrophil recovery censored on the date of his last assessment of any type

Summary statistics will include the number and percentage of censored times to neutrophil recovery, quartile times to neutrophil recovery, 95% Cls for the quartile times to neutrophil recovery, and KM "survival" percentages with 95% Cls at select milestone times (e.g., 42, 49 and 56 days).

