4.2.2 Inclusion Criteria

To be eligible for participation in the study, patients must meet all of the following inclusion criteria:

1. Be between the ages of ≥ 18 and ≤ 65 years
2. Have an established, pathologically confirmed diagnoses of AML by World Health Organization (WHO) criteria with $\geq 20\%$ bone marrow blasts based on histology or flow cytometry
3. Be newly diagnosed and previously untreated
4. Have an Eastern Cooperative Oncology Group (ECOG) performance status (PS) ≤ 2
5. Have a serum creatinine level ≤ 1.8 mg/dL
6. Have an alanine aminotransferase (ALT) and aspartate aminotransferase (AST) level ≤ 5 times upper limit of normal (ULN)

7. Have a total bilirubin level ≤ 2.0 mg/dL (unless secondary to Gilbert syndrome, hemolysis, or leukemia)
8. Have a left ventricular ejection fraction (LVEF) $>45\%$ by echocardiogram (ECHO) or multigated acquisition (MUGA) scan
9. Be nonfertile or agree to use an adequate method of contraception. Sexually active patients and their partners must use an effective method of contraception associated with a low failure rate prior to study entry, for the duration of study participation, and for at least 6 months after the last dose of study drug (see [Section 4.5.3](#)).
10. Be able to comply with the requirements of the entire study.
11. Provide written informed consent prior to any study related procedure. (In the event that the patient is re-screened for study participation or a protocol amendment alters the care of an ongoing patient, a new informed consent form must be signed.)

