Cycle 1: period of time from the first dose of study drug until the start of study drug in cycle 2 or the start of alternative AML therapy other than supportive measures such as blood product transfusions (hence a patient whose first response assessment in cycle 1 is a CRi is considered to have achieved CR if neutrophils and platelets recover prior to initiation of cycle 2 or alternative AML therapy)

Combined CR Rate: percentage of patients who achieve a combined CR following treatment with alvocidib

Combined Remission Rate: percentage of patients who achieve a combined remission following treatment with alvocidib

CR Rate: percentage of patients who achieve a CR following treatment with alvocidib (see section 7.8.1)

Dose-Limiting Toxicity: Refer to the study protocol for the specific conditions and events that qualify as a dose-limiting toxicity (DLT)

Intent-to-Treat Population: all patients enrolled in the study regardless of whether they actually received study drug and regardless of whether evidence is found indicating they failed to meet study inclusion/exclusion criteria or had other protocol violations (see section 7.1)

Minimal Residual Disease Negative: Absence of gene fusion transcripts using standardized techniques such as multiparametric flow cytometry or next generation sequencing

Neutrophil Recovery: Absolute neutrophil count ≥1x10⁹/L following the administration of study drug

Per-Protocol Population: The subset of safety patients who either (a) have at least one response assessment on study, or (b) die prior to their first scheduled response assessment; however, patients are excluded from the per-protocol population if they have an important protocol deviation, such as when evidence is found indicating they failed to meet any study inclusion/exclusion criterion (see section 7.1)

Platelet Recovery: Platelet count ≥100x10⁹/L following the administration of study drug

Prestudy: Occurrence prior to the first administration of study drug

Safety Population: The subset of intent-to-treat patients who received at least one dose or partial dose of study drug (see section 7.1)

Shift Table: two-way frequency table pairing baseline value with the most extreme post-baseline result

Study Drug: alvocidib, Ara-C (cytarabine) and mitoxantrone

Treatment Failure: failing to achieve a CR, CRi or PR following induction therapy (see section 7.8.2)

4. Introduction

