7.10.6. Platelet Recovery

Time to platelet recovery is defined for all patients and is measured from the date of first dose (Day 1) until the first day the platelet count is $\geq 100 \times 10^9 / L$ for 14 consecutive days. It is assumed that the platelet count remains above the threshold value of $100 \times 10^9 / L$ unless there is evidence that it did not. Therefore, a patient with platelet $\geq 100 \times 10^9 / L$ on Day 60 and without another assessment for >14 days will have a time to platelet recovery of 60 days.

Rules for censoring time to platelet recovery are:

- A patient with platelet count <100x10⁹/L as of the date he is lost to follow-up will
 have his time to platelet recovery censored on the date of his last assessment of
 any type
- A patient with platelet count <100x10⁹/L as of the database lock will have his time to platelet recovery censored on the date of his last assessment of any type

Summary statistics will include the number and percentage of censored times to platelet recovery, quartile times to platelet recovery, 95% CIs for the quartile times to platelet recovery, and KM "survival" percentages with 95% CIs at select milestone times (e.g., 49, 56 and 63 days).

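### Time to neutrophil and platelet recovery (SAP 7.10.5, 7.10.6) requires no prior fall below threshold, so some patients who start above it can be scored as recovering on Day 1

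*SAP*

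**What the plan says.** **Endpoint.** SAP 7.10.5 covers all patients. Time to neutrophil recovery "is measured from the date of first dose (Day 1) until the first day the absolute neutrophil count (ANC) is" at or above 1x10^9/L "for 14 consecutive days. It is assumed that the ANC remains above the threshold value of" 1x10^9/L unless something shows otherwise. SAP 7.10.6 runs in parallel for platelets, "until the first day the platelet count is" at or above 100x10^9/L "for 14 consecutive days. It is assumed that the platelet count remains above the threshold value of" 100x10^9/L.

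**Worked examples.** A neutrophil count at or above threshold "on Day 45 and without another assessment for > 14 days will have a time to neutrophil recovery of 45 days". A platelet count at or above threshold "on Day 60 and without another assessment for >14 days will have a time to platelet recovery of 60 days". The example milestones are Days 42, 49 and 56 for neutrophils and Days 49, 56 and 63 for platelets.

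**Censoring.** In both sections the rules cover only a patient whose count is below threshold at loss to follow-up or at database lock.

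**Entry.** Protocol 4.2.2 states "To be eligible for participation in the study, patients must meet all of the following inclusion criteria" and lists eleven, none on neutrophils or platelets. Of the twelve exclusions in 4.2.3, the only blood-count limit is on peripheral blasts.

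**Count schedule.** Hematology is daily while patients are hospitalized for chemotherapy (Protocol 5.2.3; dosing runs Days 1-11) and about weekly afterwards (5.2.4), or more often if clinically indicated. The Day 14 visit (5.2.5) takes blood and marrow for disease assessment but lists no hematology panel.

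**Section 3.** The SAP's definitions list describes neutrophil and platelet recovery as a count at threshold "following the administration of study drug", with no 14-day condition.

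**The concern.** The examples and milestones show that the SAP means recovery after the chemotherapy nadir. The rule as written does not say so: it accepts the first qualifying run wherever it lies. With no entry limit on counts, some patients may begin treatment at or above threshold, and for them that run can begin on Day 1, before any marrow suppression has shown itself.

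The endpoint is a listed safety endpoint, to be summarized by quartiles and Kaplan-Meier percentages. A false Day 1 value always points toward faster recovery, that is, toward less apparent marrow toxicity. With cohorts as small as three, a chance difference in starting counts could look like a difference between doses.

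**Working it through.** **1. The rule.** Recovery day = the smallest observed day d with a count at or above threshold and no observed count below threshold on days d to d+13.

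**2. The SAP's own examples.** A neutrophil count at threshold on Day 45 with no low count observed on Days 45-58 gives 45. Platelets at threshold on Day 60 with none observed on Days 60-73 gives 60. Both reproduce.

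**3. A patient starting above threshold.** Assumed path: neutrophils 3.0x10^9/L or platelets 150x10^9/L at the start, a fall to a tenth of the threshold on the day shown, and back above threshold from Day 39. Counts are daily on Days 1-11, then weekly from Day 18 or from Day 14. Each cell gives the recovery day as written / with a prior documented fall required. Neutrophils and platelets give the same results.

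| First day below threshold | Weekly from Day 18 | Weekly from Day 14 |
|---|---|---|
| 5, 8 or 11 | 39 / 39 | 42 / 42 |
| 12 or 14 | 1 / 39 | 42 / 42 |
| 15 or 18 | 1 / 39 | 1 / 42 |
| Never | 1 / no event | 1 / no event |

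A patient whose last count is on Day 5, never below threshold, also scores 1 as written and has no event under the fix. The assumption that counts stay up fills the rest of the run, and no censoring rule applies.

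So a low count observed on any day up to Day 14 breaks the Day 1 run, and the answer is then right. The error is confined to a late fall, a fall missed on Days 12-14, no fall, or exit while above threshold.

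**4. Weight of one false event.** Cohort sizes come from the sample table in SAP Appendix 2 (3, 3, 3 and 13; total 22). If k of n times are falsely 1, the reported median sits at quantile (0.5 - k/n)/(1 - k/n) of the true times. For k = 1:

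- n = 3: share 1/3 = 33.3%; (0.5 - 0.333)/0.667 = 0.25
- n = 13: share 1/13 = 7.7%; (0.5 - 0.077)/0.923 = 0.458
- n = 22: share 1/22 = 4.5%; (0.5 - 0.045)/0.955 = 0.476

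In a 3-patient cohort the reported median is about the true 25th percentile. In the larger groups it barely moves.

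**5. How many patients?** The documents give neither the share starting above threshold nor the day of fall. As a sensitivity range only, assume that the first day below threshold is normal with SD 2 to 3. P(Day 15 or later), cut at 14.5, is then 1-7% for a mean of Day 10, 11-20% for Day 12 and 40-43% for Day 14, among those starting above threshold. If 40% start above (assumed), the Day 12 case is 0.40 x 11-20% = about 4-8% of all patients, or 1 to 2 of 22. If no count at all is taken on Days 12-14, the cut moves to 11.5 and the Day 12 case becomes 57-60% of those starting above. That is an upper case, since extra counts are allowed. The assumed day drives the answer, so I rest nothing on these figures.

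**The case against.** The strongest reply is that the 14-day condition already does most of the work. Daily counts through Day 11 catch an ordinary fall, and the result is then the same with or without a new rule. That stands. A reader might infer that any pre-nadir count above threshold is scored as recovery; the 14-day condition rules that out.

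A reader might also infer from SAP Section 3, which has no duration, that everyone starting above threshold recovers at the first post-dose count. That does not hold for the timed endpoint. SAP 4.1 sends the reader to the later subsections for how endpoints are calculated, so 7.10.5 and 7.10.6 control. Section 3 describes a state, with no start date, and its natural use is the Cycle 1 definition beside it, where a CRi becomes a CR once counts recover. Importing a 14-day run or a prior fall there could change the CR rate, the SAP's primary efficacy endpoint. That part of the objection stands in full.

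Third, the impact is limited. A false Day 1 event changes a milestone percentage only if that patient's true recovery falls after the milestone. Marrow toxicity is also summarized through within-cycle minimum counts and CTCAE shift tables (SAP 7.10.4), and prolonged Grade 4 cytopenia is a DLT (Protocol 4.4.3). SAP Table 3 lists no recovery-time table. All true, and they keep the point modest.

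Last, a patient who never becomes cytopenic arguably deserves a short time, and removing such patients conditions the curve on a post-dose outcome. This is a fair caution about presentation. It does not justify mixing never low with recovered on Day 1, nor scoring as recovered a patient who fell late or died early.

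**Conclusion.** The gap is real and narrow. As written, 7.10.5 and 7.10.6 return Day 1 for a patient who starts above threshold and whose first low count comes after Day 14, whose fall on Days 12-14 goes unobserved, who never falls, or who dies or leaves while above threshold. The SAP's own examples and milestones show that this is not intended.

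Few patients are likely to be affected, but that is a judgement: the share cannot be derived from the documents. The direction is certain (faster recovery), and one event is a third of a 3-patient cohort. The endpoint is descriptive. A reader might fear for the dose decision, but the DLT, MTD and response rules do not use time to recovery.

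**What to change.** In SAP 7.10.5 and 7.10.6 only:

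- Begin the search for the 14-day run after the first documented post-dose count below threshold.
- Report, by dose level, the number of patients with no documented fall, including those who die or leave while above threshold. Keep them visible in the denominator and do not enter them as Day 1 events.

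In SAP Section 3, add only a note that the timed endpoints follow 7.10.5 and 7.10.6. Leave the recovery thresholds behind the CRi-to-CR rule as they are.

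The cost is SAP wording; the daily and weekly counts are already collected, and times that were already post-nadir do not change. The one drawback is that the recovery curve then describes only patients who became cytopenic, so it must be shown beside the count of those who did not.

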4.3.2 Study Drug Administration

Induction – Alvocidib and 7+3

- *Days 1, 2, 3:* Alvocidib at a starting dose of 20 mg/m² as a 30-minute (±10 minutes) IV bolus followed by 30 mg/m² administered as a 4-hour (±15 minutes) IV infusion (this is the starting dose for Cohort 1; see [Table 3](#) for assigned alvocidib doses per treatment cohort)
- *Day 4:* Drug-free day
- *Days 5, 6, 7: (7+3)* Daunorubicin 60 mg/m² via IV bolus of up to 15 minutes' (±5 minutes) duration each day followed immediately by;
- *Days 5, 6, 7, 8, 9, 10, 11:* Cytarabine 100 mg/m²/day via continuous 24-hour IV infusion (±2 hours for infusion duration each day)

Reinduction – Alvocidib and 5+2

Patients **with** evidence of residual leukemia defined as >5% bone marrow blasts plus >10% cellularity, based on the Day 14 (±3 days) bone marrow will be eligible to start a second induction cycle (ie, Reinduction) with alvocidib plus 5+2. The second induction cycle with alvocidib plus 5+2 will be allowed per investigator discretion.

- *Days 1, 2, 3:* Alvocidib at same dosage as during Induction
- *Day 4:* Drug-free day
- *Days 5, 6: (5+2)* Daunorubicin 45 mg/m²/day via IV bolus of up to 15 minutes' (±5 minutes) duration each day followed immediately by;
- *Days 5, 6, 7, 8, 9:* Cytarabine 100 mg/m²/day via continuous IV infusion (±2 hours for infusion duration each day)

Consolidation – HiDAC

Consolidation therapy will consist of high-dose cytarabine (HiDAC) which may be initiated at the time of hematologic recovery or within 90 days of recovery. Consolidation therapy may start before complete hematologic recovery after discussion with the Medical Monitor. It is not anticipated that all patients will undergo Consolidation therapy.

- *Days 1, 3, 5:* HiDAC 3 gm/m² IV every 12 hours (1.5 gm/m² in patients aged 60 to 65 years) (ie, a total of 6 doses over the 3-day regimen); lower starting dose may be permitted at the discretion of the Investigator and after discussion with the Medical Monitor

Patients who plan to receive chemotherapy-based consolidation should get a minimum of two cycles of Consolidation up to a maximum of four cycles. Patients proceeding to stem cell transplant for Consolidation should get one cycle of Consolidation, if possible, to ensure disease stability while transplant plans are being made.

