11.2 Sample Size

Given the design and primary objectives of this study, the sample size will be determined by the guidelines governing dose escalation/de-escalation and the identification of DLTs. As a result, the final sample size is not fixed and will not be determined by consideration of inferential analyses conducted via statistical hypothesis testing. It may be anticipated that the study sample size will be up to 40 patients. This is based on observing DLTs in 2 of 3 patients enrolled at the fourth dose level (Cohort 4) and declaring the third dose level as the MTD (3 patients each in the first and second dose levels, 6 patients in the third dose level during dose escalation, 3 patients at the fourth dose level, and an additional 20 patients at the third dose level for confirmation of safety as well as additional safety analysis and feasibility for determining MRD by dual methods [ie, MPFC and NGS] at a central laboratory). However, the actual number of patient enrolled may be slightly more or less depending on the actual pattern and frequency of DLTs.

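### Time to neutrophil and platelet recovery: the 14-day window is not closed when HiDAC starts, and death before recovery has no stated rule

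*SAP*

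**What the plan says.** SAP 7.10.5 measures time to neutrophil recovery from first dose to the first day on which ANC is at least 1x10^9/L for 14 consecutive days. The count is presumed to hold "unless there is evidence that it did not". In its example, a patient at threshold on Day 45 and "without another assessment for > 14 days will have a time to neutrophil recovery of 45 days". SAP 7.10.6 does the same for platelets at 100x10^9/L; its example patient reaches threshold on Day 60 and "without another assessment for >14 days will have a time to platelet recovery of 60 days".

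Both sections censor only patients still below threshold, at loss to follow-up or database lock: such a patient "will have his time to neutrophil recovery censored on the date of his last assessment of any type" or, for platelets, "will have his time to platelet recovery censored on the date of his last assessment of any type". The estimator is Kaplan-Meier, at milestones such as Days 42, 49 and 56 for ANC.

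Protocol 4.3.2 says that HiDAC "may be initiated at the time of hematologic recovery or within 90 days of recovery". Protocol 5.4.3 and 5.4.4 schedule hematology daily during the HiDAC admission and weekly afterwards.

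SAP Section 3 defines neutrophil and platelet recovery by threshold alone. Its Cycle 1 definition upgrades a CRi to CR if counts recover before cycle 2 or alternative AML therapy begins.

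**The concern.** The 14-day requirement screens out transient rises. It does so fairly only while nothing new is depressing the counts. Once HiDAC starts, a fall describes HiDAC and not the marrow's recovery from alvocidib plus 7+3. Read literally, the SAP still treats that fall as evidence against the earlier recovery. Patients who recover and consolidate promptly could then be recorded as slow to recover, or as not recovered. A patient could be in CR under Section 3, which needs both counts to have recovered, and yet have no induction recovery under 7.10.5 or 7.10.6.

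The second gap is death. A patient who dies below threshold can never recover. If that patient is censored, one minus Kaplan-Meier estimates recovery in a setting where nobody dies, not the share of treated patients who recovered. Both gaps affect the SAP's only time-to-recovery measures.

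**Working it through.** **1. The plan's own examples.** Take recovery as the first day d with a count at or above threshold and no lower observed count on days d to d+13. The ANC example returns 45 days and the platelet example 60 days. Both agree with the SAP.

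**2. The same Day-45 patient, now given HiDAC.** Let g be the days from recovery to HiDAC and k the days from HiDAC start to ANC below threshold. The fall comes on Day 45+g+k, and the window's last day is 45+13 = 58. The date is lost when 45+g+k ≤ 58, that is, when g+k < 14. If the next recovery is assumed to come 28 days after HiDAC start, the recorded day becomes 45+g+28.

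| g (days) | k = 5 | k = 7 | k = 10 |
|---|---|---|---|
| 0 | 73 | 73 | 73 |
| 3 | 76 | 76 | 76 |
| 5 | 78 | 78 | 45 |
| 7 | 80 | 45 | 45 |
| 10 or 14 | 45 | 45 | 45 |

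If follow-up ends 20 days after HiDAC start, before the second recovery, the patient is censored instead: at Day 65 for g = 0 and Day 68 for g = 3. The documents give neither g (only 0 to 90 days) nor k. The table also assumes that a fall is seen on the day it happens. Under weekly counts, some falls would be seen only after the window closed, and those dates would stand.

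**3. Death.** SAP 7.8.5 names death for CR duration, so the silence in 7.10.5 and 7.10.6 is not a general convention. A patient who dies below threshold fits only the database-lock rule, which censors at the last assessment. This is an inference, not a stated rule.

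Inputs:
- Recovery time: lognormal, median 33 days, log-SD 0.25. The median is a proxy from Protocol 2.6.2.2, which reports 33 days (range 22-71) for ANC over 0.5x10^9/L, a lower threshold. The log-SD is assumed.
- Death: constant hazard λ = −ln(1−p)/60. For p, 8% is 60-day death in Protocol 2.6.2.2; 10% (FLAM) and 4% (7+3) are 60-day treatment-related mortality in Protocol 2.6.2.3.

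With deaths censored, one minus Kaplan-Meier estimates F(t) = Φ(ln(t/33)/0.25). At Day 42, ln(42/33)/0.25 = 0.965 and F = 83%. The proportion who actually recover is the integral from 0 to t of f(u)·exp(−λu) du. Simulation of 400,000 patients per row gives, at Days 42/49/56:

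| 60-day death | 1−KM, % | Actually recovered, % | Difference, points |
|---|---|---|---|
| 4% | 83.4/94.4/98.3 | 81.6/92.3/96.1 | 1.8/2.1/2.2 |
| 8% | 83.2/94.3/98.2 | 79.6/90.1/93.8 | 3.6/4.2/4.4 |
| 10% | 83.3/94.3/98.2 | 78.9/89.0/92.7 | 4.4/5.3/5.5 |

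**4. Both effects together, at 8% death.** If every HiDAC gap is 14 days or more, no date is lost and the 8% row applies: overstatement of about 4 points. Now let 41% of patients consolidate (9 of 22 in the SAP Appendix 2 sample table, used only as an illustrative input), with gaps spread evenly over 0-14 days, k of 7 to 10 days and the next recovery 28 days after HiDAC start. About 15% of patients lose their date. The SAP rule gives 69.9/79.4/84.8% against 79.7/90.1/93.7% who recovered, which is 9.8/10.7/8.9 points too low. The sign turns on HiDAC scheduling.

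**The case against.** The case for leaving the text alone is that little depends on it. Protocol 11.2 says that the sample size "will not be determined by consideration of inferential analyses conducted via statistical hypothesis testing", and no dose decision uses time to recovery. Prolonged Grade 4 cytopenia has its own Day 50 and Day 60 DLT rule (Protocol 4.4.3), and CTCAE shift tables are planned (SAP 7.10.4). SAP Table 3 lists no recovery table. All of this stands and limits the importance. It does not remove the problem: SAP 4.1 names both times as safety endpoints, and with 3 to 6 patients per dose level in escalation one moved date can change a cohort's median.

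A reader might also infer more than the documents support:

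- **That Kaplan-Meier overstates recovery overall.** This is true of censored deaths taken alone. Lost dates push the curve down, and step 4 shows that the sum can go either way.
- **That every prompt consolidator, or everyone given HiDAC, loses the recovery date.** Only those with g+k under 14 do. Protocol recovery needs both ANC and platelets, so the lineage that recovers first has part of its run completed before HiDAC. The sample table's HiDAC count is not an estimate of the share affected.
- **That patients who leave with persistent leukemia add a much larger overstatement.** The sample table's lack-of-efficacy row records failure to achieve remission, not failure of count recovery, and 8 of 22 withdrawal reasons are missing. Living patients are censored at the last assessment of any type. SAP 7.8.3 describes at least 30 days of follow-up after the end-of-study visit, so many may still be at risk at Day 56, if those contacts count as assessments.

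**Conclusion.** The point holds as two limited defects. First, the 14-day window is not closed at the next cycle. HiDAC-induced falls can therefore delay or remove true induction recovery dates, in conflict with SAP Section 3. The mechanism follows from the text, but its frequency cannot be derived from the documents. Second, death before recovery is unaddressed. If it is censored, as the rules imply, Kaplan-Meier overstates the proportion recovered at Days 42 to 56 by about 2 points at 4% 60-day mortality, 4 points at 8% and 4-6 points at 10%. Those sizes rest on lognormal recovery, a constant death hazard and a proxy median, and were computed at the ANC milestones only.

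The net direction is not determined. These are descriptive safety summaries and the MTD decision is not affected. The correction is still worth making before database lock, because the reported figures would otherwise depend partly on when consolidation was scheduled.

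**What to change.** - In SAP 7.10.5 and 7.10.6, count recovery on the first day the threshold is reached and then held for 14 days or until the start of the next treatment cycle or other AML therapy, whichever comes first. The Day-45 patient then keeps Day 45 whatever the HiDAC gap. The boundary is the one that the SAP's Cycle 1 definition already uses.
- Align the Section 3 definitions of neutrophil and platelet recovery with these sections.
- State how death before recovery is handled. Report cumulative incidence of recovery (Aalen-Johansen) at the milestone days, with death and start of further AML therapy before recovery as competing events. Say explicitly whether protocol reinduction counts as further therapy or as part of induction.

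The cost is minor SAP wording and programming. The dates of counts, treatment and death are already collected. Handling death this way makes the reported recovery percentages slightly lower; closing the window restores earlier dates and works in the other direction.
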